4.1 Dose modification, interruption or discontinuation of treatment

If an adverse event is clearly associated to one of study drugs, the dose adjustment directed for that study drug will be followed; however, if the causality is not clear, then it may be necessary to adjust both study drugs. Dosing adjustments will be discussed with the sponsor. If a patient experiences a DLT then treatment with Sonidegib plus buparlisib must be stopped and the patient may be discontinued from the study. However, following resolution of the DLT to CTCAE Grade 1 or to the patient's baseline value, the patient may continue to receive study treatment with a 50% dose reduction for either sonidegib, buparlisib or both, if appropriate, at the discretion of the investigator and after discussion with the Sponsor.

If a patient requires a dose delay of > 21 days due to an sonidegib- or buparlisibrelated toxicity, then the patient must be discontinued from the study; however, if the patient is obtaining clinical benefit (ie, SD, PR, or CR), the patient may continue treatment at the same or at a reduced dose following discussion between the investigator and Novartis. All patients will be followed for AEs and SAEs for 30 days following the last dose of sonidegib and/or buparlisib. If the administration of study treatment was interrupted for reasons other than toxicity, then treatment with Sonidegib and buparlisib may be resumed at the same dose.

Patients who experience hematologic, renal, hepatic, or muscle toxicities should receive follow up and dosing modifications for sonidegib as per Table 9 and 10 below. Specific instructions for follow-up and dosing modifications for sonidegib are described in detail in Table 9. Patients who experience muscle toxicity, regardless of whether the toxicity meets the criteria described for a DLT, should be receive follow-up and dosing modifications specified in Table 9 below.

Table 9. Recommended dose modifications and dose delays for suspected sonidegib** treatment-related toxicities	
Worst toxicity CTCAE grade* (value)	During a cycle of therapy
Не	ematologic
Neutropenia (ANC)	
Worst toxicity CTCAE grade* (value)	During a cycle of therapy
Grade 1 (ANC < LLN - 1500/mm ³)	Maintain dose level
Grade 2 (ANC < 1500 - 1000/mm ³)	Maintain dose level

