Grade 3 or 4 (ANC < 1000 - 500/mm ³ or < 500/mm ³)	Omit dose until resolved to ≤ Grade 1, then: • If resolved in ≤ 7 days, implement 50% dose reduction • If resolved in > 7 days, discontinue drug • If a Grade 4 event, consider hospitalization if appropriate
Thrombocytopenia (PLT)	
Grade 1 (PLT < LLN - 75,000/mm ³)	Maintain dose level
Grade 2 (PLT < 75,000 - 50,000/mm ³)	Maintain dose level
Grade 3 or 4 (PLT < 50,000 - 25,000/mm ³ or < 25,000/mm ³)	Omit dose until resolved to ≤ Grade 1, then: •• If resolved in ≤ 7 days, implement 50% dose reduction •• If resolved in > 7 days, discontinue drug •• If a Grade 4 event, consider hospitalization if appropriate

Febrile Neutropenia	
Grade 3 (ANC $< 1.0 \times 10^9$ /L, fever \ge	Omit dose until resolved, then implement 50% dose
38.5°C)	reduction
Grade 4	Consider hospitalization
Life-threatening consequences; urgent intervention indicated	Discontinue drug

Table 9. Recommended dose modifications and dose delays for suspected sonidegib** treatment-related toxicities	
Worst toxicity CTCAE grade* (value)	During a cycle of therapy
M	uscle Toxicity
Elevated crea	atinine phosphokinase (CK)
Asymptomatic (no new-onset muscle pain/spasm or worsening of pre-existing muscle pain/spasm) CTCAE Grade 1 or 2 CK elevation	 ♦♦ For CTCAE Grade 1 CK elevation, continue treatment on same dose and continue monitoring as per schedule of assessments ♦♦ For CTCAE Grade 2 CK elevation, continue on same dose level of sonidegib. CK should be measured weekly until resolution to ≤ Grade 1.
Symptomatic (new-onset or worsening of pre-existing muscle pain/spasm) with CTCAE Grade 1 or 2 CK elevation	 ♦♦ For CTCAE Grade 1 CK with muscle pain/spasm ≥ CTCAE Grade 1, continue treatment at same dose and measure CK weekly until CK returns to normal or baseline value or muscle pain/spasm resolves ♦♦ For CTCAE Grade 2 CK with muscle pain/spasm ≥ CTCAE Grade 1, continue treatment at same dose level of sonidegib. CK should be measured weekly until CK is ≤ CTCAE Grade 1

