Grade 4 Total bilirubin > 10.0 x ULN	Discontinue study drug. Consider if hospitalization is appropriate.

Table 9. Recommended dose modifications and dose delays for suspected sonidegib** treatment-related toxicities	
Worst toxicity CTCAE grade*(value)	During a cycle of therapy
	AST or ALT
Grade 1 (> ULN - 3.0 x ULN)	Maintain dose level
Grade 2 (> 3.0 - 5.0 x ULN)	Maintain dose level
Grade 3 (> 5.0 - 20.0 x ULN)	Omit dose until resolved to ≤ Grade 1 or baseline then: •• If resolved in ≤ 7 days, then maintain dose level •• If resolved in > 7 days, then implement 50% dose reduction
Grade 4 (> 20.0 x ULN)	Omit dose until resolved to ≤ Grade 1 or baseline, then implement 50% dose reduction. Consider if hospitalization is appropriate
	Cardiac
Cardiac - prolonged QTc interval Grade 3 (QTcF > 500 msec or >60 ms from baseline on at least 2 separate ECGs taken within 1 hour)	First Occurrence: ◆ Omit dose ◆ Perform an analysis of serum potassium and magnesium, and if below lower limit of normal, correct with supplements to within normal limits. Concomitant medication usage must be reviewed. ◆ Perform a repeat ECG within one hour of the first QTcF of > 500 ms ◆ If QTcF remains > 500 ms, repeat ECG as clinically indicated but at least once a day until the QTcF returns to < 480 ms. ◆ Once QTcF prolongation has resolved, study treatment may be restarted with a 50% dose reduction Second Occurrence: ◆ discontinue patient from study drug

Cardiac - prolonged QTc interval	Discontinue patient from study drug
Grade 4	

Table 9. Recommended dose modifications and dose delays for suspected sonidegib** treatment-related toxicities	
Worst toxicity CTCAE grade* (value)	During a cycle of therapy
Otl	her Cardiac Events
Grade 1	Maintain dose level
Grade 2	Implement 50% dose reduction of buparlisib
Grade 3	Omit dose and discontinue study drug
Grade 4	Omit dose and discontinue study drug. Consider if hospitalization if appropriate
Oth	er adverse events**
Grade 1	Maintain dose level
Grade 2	Implement 50% dose reduction
Grade 3	Omit dose and discontinue study drug
Grade 4	Omit dose and discontinue study drug

Grade 3	Omit dose and discontinue study drug
Grade 4	Omit dose and discontinue study drug
	Consider if hospitalization if appropriate
111 1 110 1 1 1 1 1	i di

All dose modifications should be based on the worst preceding toxicity.

If the dose-limiting toxicity recurs in a patient following dose reduction, then further therapy with sonidegib will not be continued.

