If a patient requires a dose interruption of > 21 days from the intended day of the next scheduled dose because of a sonidegib-related toxicity, then the patient must be discontinued from the study.

*Common Toxicity Criteria for Adverse Events (CTCAE Version 4.0).

** If the investigator deems that a recommended dose reduction or the recommendation to maintain the same dose level is not in the best interest of the patient, this decision may be discussed with Novartis on a case-by-case basis.

Criteria for follow-up and dosing modifications for buparlisib are described in detail in Table 10.

For overlapping toxicities of sonidegib and buparlisib, specifically hematologic, renal and hepatic toxicities, BOTH sonidegib and buparlisib will be reduced or discontinued depending on toxicity grade per the guidelines listed below for each drug (Tables 9 and 10).

Table 10. Recommended dose modifications and dose delays for suspected buparlisib treatment-related toxicities		
Worst toxicity CTCAE grade* (value)	During a cycle of therapy	
	Hematologic	
]	Neutropenia (ANC)	
Grade 1 (ANC < LLN - 1500/mm ³)	Maintain dose level	
Grade 2 (ANC < 1500 - 1000/mm ³)	Maintain dose level	
Grade 3 or 4 (ANC < 1000 - 500/ mm ³ or < 500/mm ³)	 Omit dose until resolved to ≤ Grade 1, then: If resolved in ≤ 7 days, implement 50% dose reduction If resolved >7 days, discontinue drug If a Grade 4 event, consider hospitalization if appropriate 	
Thrombocytopena		
Grade 1 (PLT < LLN - 75 x 10 ⁹ /L)	Maintain dose level	
Grade 2 (PLT < 75 - 50 x 10 ⁹ /L)	Maintain dose level	

Grade 3 (PLT $< 50-25 \times 10^9/L$)	Omit dose until resolved to ≤ Grade 1, then:	
	 If resolved in ≤ 7 days, then maintain dose level If resolved in > 7 days, then implement 50% dose reduction 	
Grade 4 (PLT < 25 x 109/L)	Omit dose until resolved to ≤ Grade 1, then implement 50% dose reduction. Consider if hospitalization is appropriate	
	Renal	
	Serum creatinine	
Serum creatinine <1.5 x ULN	Maintain dose level	
Serum creatinine 1.5-3 x ULN	Omit dose until resolved to ≤ Grade 1, then: •• If resolved in ≤ 7 days, then maintain dose level •• If resolved in > 7 days, then implement 50% dose reduction (consider checking serum CK, if not already done)	
Table 10. Recommended dose modifications and dose delays for suspected buparlisib treatment-related toxicities		
Worst toxicity CTCAE grade* (value)	During a cycle of therapy	

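### Table 9 gives opposite sonidegib instructions for fever with ANC 500 to < 1000/mm3 when ANC recovery takes about 8 to 21 days

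*Combined protocol and SAP*

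**What the plan says.** Table 9 in section 4.1 sets out recommended sonidegib changes by toxicity and CTCAE grade. Two of its hematologic rows matter here.

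- **Neutropenia, Grade 3 or 4** (ANC below 1000/mm3, with no condition about fever): hold the drug until Grade 1 or better. If that takes 7 days or less, restart at 50%. Otherwise, "If resolved in > 7 days, discontinue drug".
- **Febrile neutropenia, Grade 3** (ANC below 1.0 x 10^9/L with fever of at least 38.5°C): "Omit dose until resolved, then implement 50% dose" reduction. The row sets no limit on recovery time and does not say what counts as resolved.

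Several general rules surround these rows:

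- The notes closing Table 9 say "All dose modifications should be based on the worst preceding toxicity". They also take a patient off study if a sonidegib-related interruption exceeds 21 days.
- The opening text of section 4.1 softens that limit for a patient with stable disease or a response, after discussion with the company supplying the drug. It also says "Dosing adjustments will be discussed with the sponsor".
- After a DLT, a 50% restart is possible "following resolution of the DLT to CTCAE Grade 1 or to the patient's baseline value", at the investigator's discretion and after sponsor discussion.
- For hematologic toxicity, "BOTH sonidegib and buparlisib will be reduced or discontinued depending on toxicity grade per the guidelines listed below for each drug".

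**The concern.** The two rows overlap and can require opposite actions for the same patient. On the febrile-row reading, one ANC course with one recovery time leads to a half-dose restart if the patient had fever and to discontinuation if not. The more serious presentation is then handled more leniently, which is hard to believe was intended. The Grade 3 neutropenia and thrombocytopenia rows just above it in Table 9 both use a Grade 1 recovery level and a 7-day limit. The febrile row has neither, so an omission is the likelier explanation.

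What is at stake is consistent dosing and safety in a small study of a two-drug combination. No endpoint definition, sample size or analysis rests on this row.

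**Working it through.** There is no planned figure to reproduce. The check is a unit conversion and a comparison of rows.

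**Overlap.** 1 L = 10^6 mm3, so 1.0 x 10^9/L = 10^9 / 10^6 = 1000/mm3. The febrile row's ANC limit is therefore the upper limit of the Grade 3 neutropenia row. Every patient with fever of at least 38.5°C and ANC 500 to < 1000/mm3 meets both rows, each at Grade 3.

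**Recovery level.** In the same table, Grade 1 neutropenia has its lower bound at 1500/mm3, so the neutropenia row's clock stops at ANC ≥ 1500/mm3.

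**Actions by recovery time.** The table takes the febrile row's undefined end-point as that same recovery level.

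| ANC nadir, with fever | Time to ≤ Grade 1 | Neutropenia row | Febrile row, Grade 3 | Result |
|---|---|---|---|---|
| 500 to < 1000 | ≤ 7 days | 50% | 50% | agree |
| 500 to < 1000 | 8 to 21 days | discontinue | 50% | **conflict, no rule to choose** |
| 500 to < 1000 | > 21 days | discontinue | 50%, overridden by the 21-day rule | discontinue, unless the clinical-benefit exception is used |
| < 500 (Grade 4 neutropenia) | ≤ 7 days | 50% | 50% | agree |
| < 500 (Grade 4 neutropenia) | > 7 days | discontinue | 50% | worst-toxicity rule, read by grade, points to discontinue |

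The 21-day limit runs from the intended day of the next dose, so the upper end is approximate.

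**Possible tie-breaks at Grade 3 against Grade 3.**

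- The worst-toxicity rule gives a tie, because the column it governs is graded by CTCAE and both events are Grade 3.
- The DLT text supplies a recovery level but leaves the restart to discretion, and the document as supplied lists no DLT criteria.
- The double-asterisk note to Table 9 begins "If the investigator deems that a recommended dose reduction or the recommendation to maintain the same dose level" and allows a case-by-case departure. It does not say which row applies.

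**Illustration (assumed values).** Temperature 38.6°C with ANC 700/mm3, and ANC reaching 1500/mm3 on day 12. Since 12 > 7, the neutropenia row discontinues sonidegib. Since 12 ≤ 21, the 21-day rule does not apply, and the febrile row restarts at 50%.

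**Frequency.** Table 2 (section 1.4.7.2.1) lists related events in at least 5% of 103 sonidegib patients, and neutropenia is absent. Because 0.05 x 103 = 5.15, at most 5 of 103 (4.9%) had it at any grade. Assuming that single-agent ceiling carries over to the 24 planned patients, 24 x 5/103 = 1.2 patients with related neutropenia of any grade. The combination rate is not given. The conflict also needs fever, a nadir of 500 to < 1000/mm3 and recovery after day 7, so the expected count should be below that ceiling.

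**The case against.** The best defence is that the rows can be applied together. Meeting the febrile row does not release a patient from the neutropenia row, and neighbouring rows define recovery as Grade 1 or better. This argues well against very early restarts, such as when fever settles while ANC is still below 1500/mm3. A reader might infer such restarts from the undefined end-point, but they arise only if the neutropenia row is set aside, so the point does not rest on them. The defence does not remove the conflict after day 7, when one row stops the drug and the other resumes it.

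A second defence is that the named febrile row is the more specific rule and should govern. That is coherent but not stated, and it produces the lenient handling of the worse event. Which action is right remains the sponsor's clinical decision.

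Third, Table 9 is advisory, the study is single-center and adjustments go to the sponsor. This stands and limits the harm, but the written guidance still contradicts itself.

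Three stronger readings are tempting and are not supported:

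- **That the conflict covers every recovery beyond 7 days.** Table 9's own 21-day rule closes it at the upper end, apart from the clinical-benefit exception.
- **That the documents say nothing about frequency.** Table 2 gives a ceiling for sonidegib alone.
- **That this row in particular leaves patients on sonidegib alone.** Table 10 would stop buparlisib after slow neutrophil recovery, so that outcome is possible. But any buparlisib-only stop, such as for Grade 3 rash, mood change or fatigue, can do the same.

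**Conclusion.** The contradiction is real but narrow. It applies to sonidegib, to fever of at least 38.5°C with ANC 500 to < 1000/mm3, and to ANC recovery in about days 8 to 21. In that window Table 9 says both to discontinue and to resume at 50%, and nothing stated chooses between them.

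The window assumes that the febrile row's end-point is Grade 1 or better, and that the worst-toxicity rule is read by grade. The expectation that few patients are affected assumes that the sonidegib single-agent experience is a fair guide to the combination.

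This is a minor clarification for dosing consistency and safety. The response-rate and duration-of-response analyses, the 12 patients per cohort and the analysis sets are unaffected.

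**What to change.** In the Grade 3 febrile neutropenia row of Table 9, replace the instruction with: *Omit dose until afebrile and ANC ≤ Grade 1; if this took ≤ 7 days, resume at 50%; if it took > 7 days, discontinue sonidegib.* This carries over the recovery level and time limit of the neutropenia row, and it removes the contradiction by itself. If the sponsor did intend the febrile row to be more lenient, the row should say so and define resolution.

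Leave Table 10 unchanged, and do not add a line there that the stricter of two rows governs. Grade 3 febrile neutropenia could fall under that table's row for other adverse events, which discontinues. Such a line could then force buparlisib to stop even when ANC recovers within 7 days, where the Table 10 neutropenia row now allows a 50% restart.

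The cost is one sentence in the next amendment, with no change to visits, sample size or analysis. The downside is that an occasional patient who might have resumed sonidegib at half dose would stop. That matters most in Cohort 2, since section 1.3 notes how limited the alternatives are for patients resistant to Smoothened inhibitors.

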CTCAE Grade 3 or 4 CK elevation (with or without muscle pain/spasm)	 ♦♦ Omit sonidegib dose, check blood myoglobin and monitor renal function. Measure CK weekly until resolution to Grade ≤ 1 ♦♦ Consider performing electromyography, MRI scan of symptomatic muscle group(s) and muscle biopsy ♦♦ If renal function is not impaired and resolution to ≤ CTCAE Grade 1 occurs within 21 days, consider resuming treatment at a reduced dose; CK should be measured weekly for 2 months after readministration of sonidegib ♦♦ Patients who experience renal impairment (serum

creatinine > 2x ULN) should be permanently
discontinued from the study
◆◆ If a Grade 4 event, consider hospitalization if
appropriate

Table 9. Recommended dose modifications and dose delays for suspected sonidegib** treatment-related toxicities	
Worst toxicity CTCAE grade* (value)	
Muscle pain/spasm (new onset or worsening of preexisting muscle pain/spasm)	 ♦♦ For CTCAE Grade 1 muscle pain/spasm, continue treatment on the same dose and planned assessments ♦♦ For CTCAE ≥ Grade 2 muscle pain/spasm, measure CK weekly until muscle pain resolves to ≤ Grade 1. If CK is elevated, follow guidance for CK elevation as described above. Continue treatment with sonidegib ♦♦ For new-onset CTCAE Grade 3 muscle pain/spasm, interrupt sonidegib. Collect blood sample for CK measurement at the time of dose interruption. Provide symptomatic treatment. Measure CK weekly until the muscle pain/spasm resolves to ≤ Grade 1 and resume therapy at a reduced dose. Measure CK weekly for 2 months after re-administration.
	Renal
	Serum creatinine
Serum creatinine <1.5 x ULN	Maintain dose level
Serum creatinine 1.5-3 x ULN	Omit dose until resolved to ≤ Grade 1, then: ◆ If resolved in ≤ 7 days, then maintain dose level • If resolved in > 7 days, then implement 50% dose reduction (consider checking serum CK, if not already done)
Grade 3 Serum creatinine > 3.0 - 6.0 x ULN	Omit dose until resolved to ≤ Grade 1 then implement 50% dose reduction
Grade 4 Serum creatinine > 6.0 x ULN	Omit dose and discontinue study drug. Consider hospitalization if appropriate
	Hepatic
	Bilirubin
Total bilirubin <1.5 x ULN	Maintain dose level

Total bilirubin 1.5-3 x ULN	Omit dose until resolved to ≤ Grade 1, then: ♦ If resolved in ≤ 7 days, then maintain dose level ♦ If resolved in > 7 days, then implement 50% dose reduction
Grade 3 Total bilirubin > 3.0 - 10.0 x ULN	Omit dose until resolved to ≤ Grade 1, then implement 50% dose reduction

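### Table 9 interrupts sonidegib for new-onset Grade 3 muscle pain but, on its plain reading, continues it when preexisting pain worsens to Grade 3 and CK is Grade 2 or below

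*Combined protocol and SAP*

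**What the plan says.** Section 4.1 sends muscle toxicity to Table 9 whether or not the event counts as a dose-limiting toxicity (DLT). The relevant row is headed "Muscle pain/spasm (new onset or worsening of preexisting muscle pain/spasm", so it takes in both kinds of pain. It has three bullets.

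- The first continues treatment for Grade 1 pain.
- The second reads "For CTCAE ≥ Grade 2 muscle pain/spasm, measure CK weekly until muscle pain resolves to ≤ Grade 1", and then "If CK is elevated, follow guidance for CK elevation as described above. Continue treatment with sonidegib".
- The third reads "For new-onset CTCAE Grade 3 muscle pain/spasm, interrupt sonidegib". It goes on to require a CK sample when dosing is interrupted, weekly CK until the pain settles, a restart at a reduced dose, and weekly CK for two months afterwards.

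The CK rows to which the second bullet refers are in the same table. For symptomatic patients they say "For CTCAE Grade 1 CK with muscle pain/spasm ≥ CTCAE Grade 1, continue treatment at same dose and measure CK weekly" and "For CTCAE Grade 2 CK with muscle pain/spasm ≥ CTCAE Grade 1, continue treatment at same dose level of sonidegib". For Grade 3 or 4 CK, with or without pain, the instruction is "Omit sonidegib dose, check blood myoglobin and monitor renal function".

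Table 9 is titled as a set of recommendations. Under its footnote, if the investigator judges that "the recommendation to maintain the same dose level is not in the best interest of the patient, this decision may be discussed with Novartis", case by case. The text before the table also says that dose changes will be discussed with the sponsor.

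**The concern.** The row heading names two kinds of patient, but the interruption rule names only one. A site that applies the table literally to a patient whose earlier muscle pain has worsened to Grade 3, with CK at Grade 2 or below, finds instructions to continue and none to interrupt. The protocol gives no reason to treat that patient differently from one whose Grade 3 pain is new.

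Patient safety is at stake. Section 1.4.2 describes muscle as a dose-limiting target of sonidegib, with CK elevation accompanied by muscle pain and raised myoglobin. It also reports one case of rhabdomyolysis with renal failure that needed hemodialysis.

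**Working it through.** No arithmetic applies. The check is to run each combination of pain history and CK level through the Table 9 rules for Grade 3 pain.

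| Grade 3 pain | CK normal | CK Grade 1 | CK Grade 2 | CK Grade 3 or 4 |
|---|---|---|---|---|
| Worsened from preexisting | Continue (second pain bullet) | Continue (second pain bullet and CK Grade 1 bullet) | Continue (second pain bullet and CK Grade 2 bullet) | Omit |
| New onset | Continue (second) and interrupt (third) | Continue (second and CK Grade 1) and interrupt (third) | Continue (second and CK Grade 2) and interrupt (third) | Omit |

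1. **Upper row.** With CK at Grade 2 or below, no Table 9 bullet interrupts dosing on the plain reading. The two symptomatic CK bullets exclude each other, so a patient meets the second pain bullet and at most one CK bullet.
2. **Lower row.** The bullets overlap without a stated order. The third bullet's own content settles the order, because a sample at interruption and a restart at a reduced dose make no sense if dosing continues.
3. **Meaning of new onset.** The table sets new onset and worsening of preexisting pain side by side as separate categories in three places: the headings for asymptomatic CK elevation, symptomatic CK elevation and muscle pain. Using the first term alone in the third bullet therefore reads as leaving out the second.
4. **Who is affected.** Pain that starts on study drug and climbs to Grade 3 can be read as new onset. The gap concerns patients who had muscle pain before treatment.
5. **Other rules in Section 4.1.** The note basing modifications on the worst preceding toxicity sets no different action. The DLT stop rule could apply, but the documents give no DLT criterion for muscle pain. The footnote and the sponsor discussion permit a departure without setting a default action.

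**The case against.** **The phrase may already cover worsening.** New-onset Grade 3 pain can mean pain newly reaching Grade 3. Section 4.3.3 offers some support, because it defines intolerable toxicity through Grade 3 or 4 events that were not present at baseline. On that usage, Grade 1 pain at baseline that rises to Grade 3 is a new Grade 3 event and the third bullet applies. This reading is tenable. It competes with the table's own separation of the two categories, so the text stays ambiguous on a dosing instruction.

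**Table 10 may catch the patient.** Section 4.1 mentions both tables for muscle toxicity. Table 10 has no muscle row, and its row for other adverse events omits and discontinues study drug at Grade 3. Section 5.1 defines study drug as the combination, and Section 4.3.3 attributes events to the combination unless another cause is clear. A site might therefore apply that row if it also suspects buparlisib. But Table 9 is the specific rule for sonidegib, and the clause that applies both tables to overlapping toxicities names hematologic, renal and hepatic events, not muscle.

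**Safeguards exist.** The second bullet requires weekly CK, and Grade 3 or 4 CK leads to omission. Section 3.2.2.2 excludes raised baseline CK and requires statins to be stopped, and Appendix B excludes neuromuscular disorders. These stand and keep the risk small. The CK rules act on CK, however, not on Grade 3 pain.

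**Stronger readings that a reader might infer.** One is that Table 9 gives a real contradiction for new-onset Grade 3 pain; the third bullet's content rules that out. Another is that protecting a patient with worsened pain always means departing from the protocol; the alternative reading of new onset and the Table 10 route both prevent that conclusion. A third is to count the continue bullets against the single interruption bullet; the count would mislead, because the two CK bullets cannot both apply to one patient.

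**Conclusion.** The point holds as a minor wording fault in a dosing rule. On the plain reading, preexisting muscle pain that worsens to Grade 3 with CK at Grade 2 or below is continued on sonidegib, while new-onset pain of the same grade is interrupted. The overlap for new-onset pain needs only clarification.

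The conclusion rests on giving new onset in the third bullet the meaning it has in the headings. If it means newly reaching Grade 3, the gap closes in substance and what remains is unclear wording.

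The affected group is narrow: patients with muscle pain before treatment that worsens to Grade 3, is suspected to be sonidegib-related and leaves CK at Grade 2 or below, in a study planned for 12 + 12 = 24 patients. The documents give no frequency of Grade 3 muscle pain at 200 mg daily, so no patient count can be stated. No endpoint or analysis is affected.

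**What to change.** Reword four bullets in two rows of Table 9.

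1. Muscle pain row, second bullet: limit it to Grade 2 pain, keeping the weekly CK and the instruction to continue.
2. Muscle pain row, third bullet: begin it *For new-onset Grade 3, or worsening to Grade 3, muscle pain/spasm, interrupt sonidegib*, and leave the rest as it is.
3. Symptomatic CK Grade 1 or 2 row, both bullets: replace the open-ended pain range with *muscle pain/spasm of CTCAE Grade 1 or 2*, and refer Grade 3 pain to the third bullet of the muscle pain row.

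This also removes the overlap for new-onset pain. The cost is that an occasional patient with worsened preexisting pain will have an interruption and then a reduced dose, with the CK checks already written into the third bullet. No new type of test is needed.
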